Golimumab in juvenile idiopathic arthritis (JIA) - associated uveitis unresponsive to adalimumab

NCT ID: 31-301ex18/19
NCT04200833

Index

1	Background	3
2	Aim.....	4
	The aim of the study is to evaluate the effectiveness of golimumab in patients with JIA associated Uveitis that experienced a treatment failure to ADA	4
3	Patients	4
4	Outcome measures	4
	4.1 Main outcome measures.....	4
	4.2 Secondary Outcomes.....	5
5	Methods.....	5
6	Statistics	5
	6.1 Scheduled Evaluations	5
	6.1 Sample size.....	6
7	Data protection	6
8	Benefit-Risk ratio	6
9	References	6

1

Background

Uveitis is a potentially blinding complication of juvenile idiopathic arthritis (JIA) [1–3]. Early and complete control of ocular inflammation in JIA is important. Treatment moves step-by step, starting with topical and/or systemic steroids and followed by conventional disease-modifying anti-rheumatic drugs (cDMARDs), usually methotrexate (MTX). In refractory cases treatment with anti-tumor necrosis factor (TNF)- α agents is recommended [4, 5]. Among these adalimumab (ADA), a fully humanised antibody against TNF- α and the only TNF- α inhibitor approved for uveitis as of 2021, has become the drug of choice. ADA shows efficacy in around 75% of patients in the first 18 months of treatment [6, 7]. In case of no response or loss of response to ADA, a switch to another biological agent is recommended [5, 8, 9]. However, the choice of biological drug *is* not clearly defined. The question remains: Is persistence in an attack on the TNF- α pathway promising in these patients? In this regard data from small numbers of patients provide evidence that switching to a second anti-TNF agent may be beneficial [8, 10]. As such golimumab (GLM), another fully humanised anti-TNF- α monoclonal antibody approved for the treatment of polyarticular JIA, has shown promising results in small heterogeneous case series [11–13].

Abbreviations:

- *JIA* *Juvenile idiopathic arthritis*
- *Anti-TNF* *anti- tumor necrosis factor*
- *ADA* *Adalimumab*
- *GLM* *Golimumab*
- *SUN* *Standardization of Uveitis Nomenclature*

2 Aim

The aim of the study is to evaluate the effectiveness of golimumab in patients with JIA associated Uveitis that experienced a treatment failure to ADA

3 Patients

Patients that suffered a loss of response to ADA and were subsequently switched to GLM from November 2012 to February 2019 will be included. Patients diagnosed and treated in the department of pediatric rheumatology and the uveitis clinic of the Medical University of Graz are eligible. Due to the retrospective nature and the classification as orphan disease no sample size calculation is feasible; a sample size of around 10 patients is to be expected.

Inclusion Criteria:

- Patients diagnosed with JIA according to the ILAR-criteria and associated Uveitis
- Golimumab treatment following treatment with
- Age between 1 and 25 years

Exclusion Criteria:

- Patient not fulfilling diagnostic criteria of a JIA associated
- Patients that were not previously treated with ADA

4 Outcome measures

4.1 Main outcome measures

The main outcome measures are assessed at predefined time points (month 1, month 3 and every 3 months thereafter) including intraocular inflammation as determined by anterior chamber cell count, best-corrected visual acuity (BCVA), corticosteroid-sparing potential, and ocular complications. Results of slit-lamp examination, applanation tonometry, ophthalmoscopy, fluorescein angiography, and spectral-domain optical coherence tomography were evaluated. Anterior chamber

(AC) cells and vitreous haze (VH) are graded by SUN criteria [16]. BCVA is determined using a Snellen chart.

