4.2 Secondary Outcomes

- Demographic data of patients
- JIA-subtype
- anatomically localization of uveitis
- Uveitis complication
- medication
- ophthalmological investigations, including visual acuity, intraocular pressure, fundoscopic findings
- Laboratory parameters under treatment (whole blood count, lever and kidney enzymes, CRP, autoimmune lab (ANA, ds-DNA, anti-drug-Ab, RF, HLA-B27.

5 Methods

A single-centre, retrospective study in patients with JIA-associated uveitis who were treated with GLM for active uveitis that had proved refractory to at least one cDMARD and to ADA.

6 Statistics

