6.1 Scheduled Evaluations

Descriptive statistics will be used. Continuous data will be evaluated via median and quartiles or mean and standard deviation, with respect to the data distribution. Categorical data will be given as absolute and relative proportions. Differences between groups will be evaluated with chi-square or fisher exact test. Time to treatment failure will be evaluated via Kaplan-Meier plots.

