6.1 Sample size

Due to scarce data (JIA associated uveitis is an orphan disease) no sample size calculation is feasible. A number of 10 patients is to be expected. The nature of the study is explorative.

7 Data protection

All patients will be given a numerical code. The data files will be saved in a secure computer at the department of pediatrics and analyzed pseudo-anonymously.

8 Benefit-Risk ratio

Therapeutic options after treatment failure of ADA for JIA associated uveitis are limited and the risk of ocular complications is high. Thus, these patients are in high need for effective treatment options. The data of the present study can help guide physicians in their choice of treatment in such cases.

A better informed treatment might reduce the burden of systemic steroids and reduce uveitis complications with their associated vision loss. In addition, data from this study might serve as a pilot for further studies.

As this is a retrospective study no risk of harm to the study population is to be expected. All data have been collected in advance and patients have been treated according to international guidelines. Thus the risk-benefit ratio is to be judged favourably.

9 References

2. Heiligenhaus et al. Interdisziplinäre Leitlinie zur Diagnostik und antientzündlichen

Therapie der Uveitis bei juveniler idiopathischer Arthritis. AWMF online
1/2018

3. Palmou-Fontana et al. Golimumab in refractory uveitis associated to juvenile idiopathic arthritis: multicentre study of 7 cases and literature review., Clin Exp Rheumatol. 2018

4. Cordero-Coma et al. Anti-tumort necrosis factor- α therapy in uveitis. Survophthal. 2015

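### AC cells and steroid sparing are summarised separately and cDMARD change is in no main outcome, so improvement cannot be read against changes in co-medication

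*Combined protocol and SAP*

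**What the plan says.** Section 4.1 sets out four main outcomes side by side: "intraocular inflammation as determined by anterior chamber cell count, best-corrected visual acuity (BCVA), corticosteroid-sparing potential, and ocular complications". They are assessed at month 1, month 3 and three-monthly after that, and AC cells are graded on the SUN scale. The section gives no response threshold and no definition of steroid sparing. It has no rule for a cell grade recorded after co-medication has been raised or lowered.

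Section 4.2 lists medication as a secondary item in one word, without doses, dates or drug classes. It is the only place where a change in cDMARD could be recorded.

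Section 5 describes a single-centre retrospective study, with no comparator, of patients "treated with GLM for active uveitis that had proved refractory to at least one cDMARD and to ADA".

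Section 6.1 (Scheduled Evaluations) states "Descriptive statistics will be used" and "Time to treatment failure will be evaluated via Kaplan-Meier plots". Failure is not defined. Chi-square or Fisher tests between groups are mentioned, but no groups are named. Section 6.1 (Sample size) adds "A number of 10 patients is to be expected" and calls the study exploratory.

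**The concern.** The stated aim (section 2) is the effectiveness of golimumab after adalimumab failure. Without a control arm, a change in other uveitis treatment is a direct alternative explanation for a change in the eye. Section 1 itself describes steroids and cDMARDs as the earlier treatment steps, so patients who start golimumab with active uveitis may well be on them or have them adjusted. The documents do not say how often.

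Two separate summaries, one of cell grade and one of steroid use, do not show whether the patients who improved are the same patients whose steroid was raised. They also do not show whether the patients whose steroid was cut kept a quiet eye. For cDMARDs there is not even a second main outcome to compare.

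Section 8 expects the data to help physicians choose treatment and to serve as a pilot, and it names a lower steroid burden as a hoped-for benefit: "A better informed treatment might reduce the burden of systemic steroids". Both uses need to know whether control of the eye and steroid reduction occurred in the same patients.

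**Working it through.** The plan states no response rate, escalation rate or power figure, so there is no figure of its own to reproduce. The only documented input is n = 10 (section 6.1, Sample size). All other counts below are assumptions chosen to show scale.

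**1. Weight of one patient.** 1/10 = 10 percentage points, in either direction.

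**2. What separate totals leave open.** Assume 7 of 10 patients improve in AC cells and 3 of 10 have steroid or cDMARD raised. The number in both categories lies between max(0, 7 + 3 − 10) = 0 and min(7, 3) = 3. All four possibilities give the same separate summaries:

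| Improved and escalated | Improved without escalation | Rate | Exact (Clopper-Pearson) 95% CI |
|---|---|---|---|
| 0 | 7/10 | 70% | 35–93% |
| 1 | 6/10 | 60% | 26–88% |
| 2 | 5/10 | 50% | 19–81% |
| 3 | 4/10 | 40% | 12–74% |

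The unadjusted rate is 70% in every row. The escalation-free rate spans 30 points, and only a per-patient cross-table shows which row applies.

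**3. Possible inflation if escalation is the only thing happening.** Let p be the response rate without escalation and e the share of the remaining patients whose eye quietens after escalation. The apparent rate is p + (1 − p)e. The chance of at least one such patient among 10 is 1 − [1 − (1 − p)e]^10.

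| p | e | Apparent rate | Excess, points | Chance of at least one |
|---|---|---|---|---|
| 30% | 10% | 37% | 7 | 52% |
| 30% | 30% | 51% | 21 | 91% |
| 30% | 50% | 65% | 35 | 99% |
| 50% | 10% | 55% | 5 | 40% |
| 50% | 30% | 65% | 15 | 80% |
| 50% | 50% | 75% | 25 | 94% |

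Over this assumed grid the excess is 5 to 35 points.

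**4. The other direction.** Step 3 covers escalation only. If steroids are tapered on golimumab, some eyes will show more cells than they would have at an unchanged dose, and the unadjusted cell result then understates the effect. The two influences can offset each other. The documents give neither rate, so the net sign cannot be derived.

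**The case against.** A reader might infer that the plan counts a patient whose eye quietens on more steroid as a golimumab success. The documents do not support that. They define no success, responder or target grade, and they do not say how a grade after escalation is handled. The gap is a missing rule.

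A reader might also infer that the main inflammation result is biased in favour of golimumab. That too is unsupported, since tapering would push the cell grades the other way.

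The strongest defence concerns steroids. Steroid sparing is itself a main outcome, so an increase would appear there as an unfavourable result and need not be hidden. Undefined treatment failure might also turn out to include escalation. The uveitis had already proved refractory to at least one cDMARD, which makes quieting through a cDMARD somewhat less plausible, although a different one could have been added. The study is descriptive and exploratory, no test of this outcome is specified, and the intervals in step 2 overlap heavily.

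Most of this stands, and it limits the point. It does not remove it: visibility in a separate summary is not a per-patient link, a cDMARD change is in no main outcome, and an undefined failure event guarantees nothing.

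There is also a fair objection to one possible remedy. If any increase since the switch made a patient a non-responder at every later visit, a brief early rise that was later fully withdrawn would count as permanent non-response. A cDMARD raised for arthritis would count against the eye. That rule is therefore too strict for the main presentation.

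**Conclusion.** The point holds as a gap in definition and presentation. As written, the plan cannot show whether the patients whose AC cells improved are those whose steroid or cDMARD was raised, or whether steroid reduction was achieved with a controlled eye. In an uncontrolled study, improvement after escalation could then be credited to golimumab, and steroid reduction with a worse eye could look favourable.

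The certain part of the size is 10 points per affected patient, if 10 patients are enrolled as expected. The 40% to 70% span and the 5 to 35 point excess rest entirely on assumed counts and rates. The net direction is unknown. No error rate is affected and the study is not invalidated, but a main outcome would be hard to interpret when a modest change to the analysis would make it readable. Even with that change, golimumab's effect is not isolated, because there is still no control.

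**What to change.** Before analysis, add the following to section 6.1 (Scheduled Evaluations):

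- At each scheduled visit, cross-tabulate per patient the SUN AC cell change against the concurrent change since golimumab start in topical or systemic corticosteroid (lower / same / higher), and against change in cDMARD or other uveitis drugs (no increase / increase).
- Beside the unadjusted cell-grade result, report the proportion improved with no corticosteroid, cDMARD or other uveitis drug above its level at golimumab start at that visit. Fix the SUN threshold for improvement beforehand.
- Report the stricter version, in which any increase since the switch counts as non-response, only as a sensitivity analysis.
- State whether such escalation counts as an event in the Kaplan-Meier analysis of time to treatment failure.

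The cost is SAP wording, a few derived variables and one table per visit for about 10 patients; no treatment changes. There are two downsides. The reported response rate may be lower. The derivation also needs dated medication detail, including topical use, which section 4.2 does not itemise, so its availability in the charts should be checked first and any gaps reported.

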4.2 Secondary Outcomes

- Demographic data of patients
- JIA-subtype
- anatomically localization of uveitis
- Uveitis complication
- medication
- ophthalmological investigations, including visual acuity, intraocular pressure, fundoscopic findings
- Laboratory parameters under treatment (whole blood count, lever and kidney enzymes, CRP, autoimmune lab (ANA, ds-DNA, anti-drug-Ab, RF, HLA-B27.

5 Methods

A single-centre, retrospective study in patients with JIA-associated uveitis who were treated with GLM for active uveitis that had proved refractory to at least one cDMARD and to ADA.

6 Statistics

6.1 Scheduled Evaluations

Descriptive statistics will be used. Continuous data will be evaluated via median and quartiles or mean and standard deviation, with respect to the data distribution. Categorical data will be given as absolute and relative proportions. Differences between groups will be evaluated with chi-square or fisher exact test. Time to treatment failure will be evaluated via Kaplan-Meier plots.

6.1 Sample size

Due to scarce data (JIA associated uveitis is an orphan disease) no sample size calculation is feasible. A number of 10 patients is to be expected. The nature of the study is explorative.

7 Data protection

All patients will be given a numerical code. The data files will be saved in a secure computer at the department of pediatrics and analyzed pseudo-anonymously.

8 Benefit-Risk ratio

Therapeutic options after treatment failure of ADA for JIA associated uveitis are limited and the risk of ocular complications is high. Thus, these patients are in high need for effective treatment options. The data of the present study can help guide physicians in their choice of treatment in such cases.

A better informed treatment might reduce the burden of systemic steroids and reduce uveitis complications with their associated vision loss. In addition, data from this study might serve as a pilot for further studies.

As this is a retrospective study no risk of harm to the study population is to be expected. All data have been collected in advance and patients have been treated according to international guidelines. Thus the risk-benefit ratio is to be judged favourably.

9 References

2. Heiligenhaus et al. Interdisziplinäre Leitlinie zur Diagnostik und antientzündlichen

Therapie der Uveitis bei juveniler idiopathischer Arthritis. AWMF online
1/2018

3. Palmou-Fontana et al. Golimumab in refractory uveitis associated to juvenile idiopathic arthritis: multicentre study of 7 cases and literature review., Clin Exp Rheumatol. 2018

4. Cordero-Coma et al. Anti-tumort necrosis factor- α therapy in uveitis. Survophthal. 2015
